1. INTRODUCTION

This document outlines the statistical methods to be implemented during the analysis of data collected within the scope of Zealand Pharma A/S ZP4207-16136 (ZEA-DNK-01711) observational trial. The purpose of this plan is to provide analysis strategies for all trial data which were collected, as well as to provide specific guidance how to analyze data for the statistical analysis.

Any deviations from this plan will be documented in the clinical study report (CSR).

2. STUDY DOCUMENTS

The following study documents are used for the preparation of the SAP:

- Protocol version 1, 18 JAN 2017
- Amendment 1, 08 May 2017
- Amendment 2, 21 AUG 2017
- Protocol version 3, 21 AUG 2017
- eCRF version 4.0, 05 DEC 2017
- Data Management Plan version 1.1, 18 Sep 2017

3. STUDY OBJECTIVES

The present trial aims to evaluate that immunogenicity risk with an assessment of the occurrence of ADAs and neutralizing ADAs, and of cross-reactivity with native glucagon, following repeated single doses of dasiglucagon by s.c. administration in T1DM patients. The trial further aims to evaluate the pharmacodynamics and pharmacokinetic responses and to correlate the consequence of an antibody response, if any, to pharmacodynamic and pharmacokinetic endpoints. The reference product in this trial is GlucaGen®, a recombinant human glucagon approved for the treatment of the severe hypoglycemic reactions that may occur in the management of insulin-treated children and adults with diabetes mellitus.

Primary objective

The primary objective is to describe the immunogenicity of repeated single doses of dasiglucagon and GlucaGen® following s.c. administration in T1DM patients.

Secondary objectives

The secondary objective consists of analyzing the safety, tolerability and pharmacodynamic response of repeated single doses of dasiglucagon following s.c. administration compared with s.c. GlucaGen® in T1DM patients.

4. STUDY DESIGN AND PLAN

This is a randomized, double-blind, parallel group, multicenter (EU, US, Canada) trial evaluating the immunogenicity of **3 fixed doses** of either **dasiglucagon or GlucaGen®** administered to **euglycemic T1DM patients**.

Blinding: Handling, preparation and administration of trial medication is done by unblinded trial personnel. All trial assessments on the trial site are done by blinded trial personnel. However, exposure assessments and ADA assessments are performed by unblinded personnel at the specialty laboratories, to make sure that dasiglucagon or GlucaGen® administration is matched with the applicable bioanalytical assay.

Patients with T1DM are randomized 1:1 to receive 3 s.c. injections of either dasiglucagon (0.6 mg) or GlucaGen® (1 mg), with 1 week between each dose. Patients are followed for at least 3 months from the day of the first dose to assess any immune response. Patients with previous exogenous glucagon exposure are not excluded from the trial, but the information on previous glucagon administration is recorded to enable subgroup analyses. A total of 90 patients should participate in and complete the trial (45 in each treatment arm). To qualify as completed, the patient must have been dosed according to protocol and have blood drawn for the ADA analyses. Prematurely discontinued patients are not replaced in order to reach 90 completed patients (see Amendment 2). 112 patients in total are to be randomized and treated.

For the safety and well-being of the patients, they are not brought into hypoglycemia prior to dosing. Prior to administration of trial product patients must reach a target plasma glucose level of 70-150 mg/dL.

The trial includes the following periods (as illustrated in figure below).

[figure not shown]

Figure 1: Overview of the trial design

The study includes the following periods:

- A screening period from day -30 to day -3 (V1)
- A treatment period, from day 0 (day of randomization), day 7 to day 14 (day of third and final dosing with trial medication), with s.c. trial medication administered on day 0, day 7, and day 14.
- A follow-up period, from the end of the treatment period, with follow-up visits at day 35, day 60, and day 104 (the EoT visit).

The overall duration of the study is about half a year from study initiation (i.e., first subject enrolled, March 2017) to study completion (i.e., last subject last visit, February 2018). The subject participation period is 3 months from enrollment to subject completion (i.e., last study visit), unless prematurely discontinued.

Key inclusion criteria at screening:

(for a complete listing of inclusion criteria please refer to the study protocol)

Subjects of any age who meet ALL of the following criteria are eligible for this study and who are willing and able to comply with the requirements of the protocol:

To be included in the trial, patients have to fulfill all of the following criteria:

- Age between 18 and 70 years, both inclusive
- Male or female patients with T1DM for at least 1 year. Diagnostic criteria as defined by the American Diabetes Association
- Hemoglobin A_{1c} (HbA_{1c}) <10%
- Stable antidiabetic treatment for at least 1 month (e.g. within 10% insulin dose adjustment)

Key exclusion criteria at screening

(for a complete listing of exclusion criteria please refer to the study protocol)

Subjects who meet **ANY** of the following criteria are not eligible for this study:

- Previous administration of dasiglucagon (previously referred to as ZP4207).
- Known or suspected allergy to trial medication(s) or related products
- History of anaphylaxis or symptoms of severe systemic allergy (such as angioedema)
- Patients on a closed loop artificial pancreas
- Receipt of any investigational drug within 3 months prior to screening
- Active malignancy within the last 5 years
- Congestive heart failure, New York Heart Association class II-IV
- Inadequately treated blood pressure as defined as systolic blood pressure ≥ 160 mmHg or diastolic blood pressure ≥ 90 mmHg at screening.
- Current bleeding disorder, including use of anticoagulant treatment
- Known presence or history of pheochromocytoma (i.e. adrenal gland tumor) or insulinoma (i.e. insulin-secreting pancreas tumor)
- Known or suspected HIV infection
- Use of a systemic beta-blocker drug, indomethacin, warfarin or anticholinergic drugs in the previous 28 days before Day 1 of this trial)
- Use of systemic corticosteroids, anti-inflammatory biological agents, kinase inhibitors or other immune modulating agents within the last 3 months prior to screening
- Aspartate aminotransferase (AST) or alanine aminotransferase (ALT) >2.5 X the upper limit of normal (ULN), bilirubin >1.5 X ULN, estimated glomerular filtration rate (eGFR) <30 mL/min/1.73m² according to the Modification of Diet in Renal Disease (MDRD) Study definition. Altered electrolytes values of clinical relevance for cardiac conduction, as judged by the investigator.
- Clinically significant abnormal ECG at screening, as evaluated by Investigator
- Donation of blood or plasma in the past month, or in excess of 500 mL within 12 weeks prior to screening
- A positive result in the alcohol and/or urine drug screen at the screening visit. Significant history of alcoholism or drug abuse as judged by the investigator or consuming more than 24 g alcohol per day for men, or more than 12 g alcohol per day for women.
- Patients with mental incapacity or language barriers that preclude adequate understanding or cooperation, who are unwilling to participate in the trial, or who in the opinion of the Investigator should not participate in the trial
- Surgery or trauma with significant blood loss within the last 2 months prior to screening
- Use of prescription or non-prescription medications known to cause QT prolongation

The following flow chart shows the investigations undertaken in this trial:

Trial period	Screening	Treatment			Follow-up		
Visit number	V1	V2	V3	V4	V5	V6	V7 (EoT)
Trial day	-3	0	7	14	35	60	104
Visit window (days)	-30 to -3		±1	±1	±2	±5	±10
Patient related info/assessments							
Informed consent	X ¹						
Inclusion/exclusion criteria	X	X ^{2,3}					
Demography	X						
Body measurements	X						
Medical history	X						
Concomitant illness	X						
Prior medications	X						
Concomitant medication	X	X	X	X	X	X	X
History of alcohol/drug abuse	X						
Randomization		X					
Withdrawal criteria		X	X	X	X	X	
Dosing day exclusion criteria		X	X	X			
Safety assessments							
Physical examination	X						X
Vital signs	X	X ¹²	X ¹²	X ¹²	X		X
ECG	X	X ¹⁰	X ¹⁰	X ¹⁰	X		X
Local tolerability		X ⁵	X ⁵	X ⁵			
Adverse events	X	X	X	X	X	X	X
Laboratory							
Hematology, biochemistry, coagulation	X ⁴	X ⁴		X ⁴	X		X
Pregnancy test	X ¹¹	X ¹¹	X ¹¹	X ¹¹			
Urinalysis	X	X ²		X ²			X
Urine drug screen	X ⁶	X ^{2,6}	X ^{2,6}	X ^{2,6}			
Alcohol breath test	X	X ²	X ²	X ²			
Exposure and pharmacodynamics (PD)							
Dasiglucagon /glucagon		X ⁷		X ⁷			
Plasma glucose		X ⁸		X ⁸			
Other assessments							
Antibodies against dasiglucagon /glucagon		X ²	X ²	X ²	X	X	X
Trial material							
Administration of trial medication		X ⁹	X ⁹	X ⁹			

ECG = electrocardiogram; EoT = End of Trial; ; PD = pharmacodynamics; V = visit

¹ Informed consent can be obtained on the same day as screening, but prior to any trial-related procedures ² Pre-dose

³ Only check of changes between the screening visit and V2.

⁴ Coagulation parameters are measured at screening visit only. On dosing days Visit 2 and 4, blood samples are collected pre-dose, and at 30 and 90 min post-dosing. The actual time for sampling should not deviate from the nominal time by more than ± 5 min. Pre-dose is defined as within 5 min prior to dosing.

⁵ Local tolerability assessed at 0.5 and 2 h post-dose. The actual time for assessment should not deviate from the nominal time by more than ± 10 min.

⁶ Urine drug screen will be performed at trial site for visits 1-4

⁷ Pre-dose, 5, 10, 30, 60, and 90 min post-dosing. The actual time of blood sampling for exposure should not deviate from the nominal time by more than ± 1 min. Pre-dose is defined as within 5 min prior to dosing.

⁸ Pre-dose, 5, 10, 30, 60, and 90 min post-dosing. The actual time for blood sampling for plasma glucose should not deviate from the nominal time by more than ± 1 min. Pre-dose is defined as within 5 min prior to dosing.

⁹ Prior to administration of trial medication patients must reach a target plasma glucose level of 70-150 mg/dL. Plasma glucose levels may be adjusted by administration of a fast-acting insulin analog or by glucose ingestion at the discretion of the investigator. At visit 2 and 4 patients must be fasting for 90 min after administration of trial medication. At all dosing visits, patients will be treated individually to alleviate any potential side effects and will be observed for at least 5 h post-dose.

¹⁰ On dosing days Visit 2, 3 and 4 ECG's are assessed pre-dose, and at 20, 35, 45 and 60 min post-dosing. The actual time of assessment should not deviate from the nominal time by more than ± 5 min. Pre-dose is defined as within 5 min prior to dosing.

¹¹ Pregnancy test is only applicable for women of childbearing potential. At Visit 1 a serum pregnancy test should be performed. At Visit 2, 3 and 4 a pre-dose urine pregnancy test should be performed.

¹² On dosing days Visit 2, 3, and 4 vitals signs are collected pre-dose and at 30, 90 and 120 min post-dosing. The actual time of assessment should not deviate from the nominal time by more than ± 5 min. Pre-dose is defined as within 5 min prior to dosing.

Table 1: Flow chart

5. DETERMINATION OF SAMPLE SIZE

The purpose of the present trial is to generate data describing the immunogenic potential of dasiglucagon and GlucaGen®. The ADA assays to be used in this trial are both validated, but specific for GlucaGen® and dasiglucagon, and the performance of the assays are thus not directly comparable. As a consequence, a formal comparison or non-inferiority analysis will not be performed.

Currently, no ADA incidences have been detected in the completed clinical trials, where up to 5 repeated doses of dasiglucagon have been administered to the same patients within a week. Across the two phase I clinical trials and a completed phase II PK/PD trial, a total of 141 subjects have been exposed to dasiglucagon and no incidences of ADA development have been observed. The obtained data indicate that dasiglucagon has a low risk for induction of ADAs in the investigated settings and as a consequence a meaningful sample size to compare both treatments cannot be estimated.

The sample size is therefore based on a certain precision of the confidence interval for the overall ADA incidence if no events are observed, respectively to ensure a certain probability for observing one event.

When no events are observed, to obtain an upper bound of 0.050 on the 90.0% confidence interval for the probability of such a rare event, would require a sample size of 45. Respectively, accepting a chance of observing at least one event of 90% and an actual probability of the event of 5%, leads to a sample size of 45 patients completing the trial. In order to account for drop-outs, it is expected that 112 patients in total will be randomized and treated.

6. GENERAL ANALYSIS CONSIDERATIONS

The statistical analyses will be reported using summary tables, listings, and figures (TLFs). The International Conference on Harmonization (ICH) numbering convention will be used for all TLFs.

Continuous variables will be analyzed using standard descriptive measures as number of non-missing observations, mean, standard deviation, median, minimum and maximum. Other summaries (e.g. quartiles, 95% confidence intervals, SEM) may be used as appropriate and will be indicated in the respective sections. Categorical variables will be summarized by counts and by percentage of patients in corresponding categories. Percentages for missing values are not displayed as they do not account for the percent calculation of other non-missing categories. Percentages are therefore routinely based on the total category count excluding the missing category. Percentages showing a rate relative to the total number of patients in this group are given in special tables (e.g. adverse event tables). Footnotes will specify the percent basis in those cases.

Individual patient data obtained from the case report forms (CRFs), central clinical laboratory, ECG, pharmacokinetic/ pharmacodynamic and immunogenicity data, and any derived data will be presented by patient in data listings.

Tabulations will include in general a total summary column, if more than one column is presented in the table.

The analyses described in this plan are considered *a priori*, in that they have been defined prior to database lock. Any analyses performed subsequent to database lock will be considered post-hoc and exploratory. Post-hoc analyses will be labeled as such on the output and identified in the CSR.

All analyses and tabulations will be performed using SAS[®] Version 9.4 or higher. Determination of Pharmacokinetic (PK) and Pharmacodynamic (PD) metrics will be performed using WinNonLin[®] Version 5.4 or using SAS[®] Version 9.4 or higher. Tables, listings, and figures will be presented in ASCII format. Upon completion, all SAS[®] programs will be validated by an independent programmer. In addition, all program output will undergo a senior level statistical review. The validation process will be used to confirm that statistically valid methods have been implemented and that all data manipulations and calculations are accurate. Checks will be made to ensure accuracy, consistency with this plan, consistency within tables, and consistency between tables and corresponding data listings. Upon completion of validation and quality review procedures, all documentation will be collected and filed by the project statistician or designee.

7. NOTATION OF TREATMENT GROUPS, TYPES, HAEMOPHILIA SEVERITY GRADING AND VISITS

7.1 Notation of treatment groups

The following notations of dasiglucagon and GlucaGen[®] treatment and other important stratification criteria are mentioned below and will be used throughout the statistical analysis.

Full notation (as used in the study protocol)	Notation as used throughout all tables, listings and figures
Dasiglucagon (ZP4207): Liquid formulation, 0.6 mL in a strength of 1 mg/mL, Single use pre-filled syringe (Zealand Pharma A/S, Glostrup (Copenhagen), Denmark)	dasiglucagon
GlucaGen [®] : Recombinant glucagon hydrochloride, Powder and solvent for reconstitution as 1 mL solution for injection in a strength of 1 mg, powder and solvent for reconstitution packed together in a plastic box. A “hypo-kit” (Novo Nordisk A/S, Bagsværd, Denmark)	GlucaGen

7.2 Visit terminology

Visit	Notation as used throughout all tables, listings and figures	Study part
Visit V1: Screening visit*, trial day -3, visit window (-30 to -3)	Screening	Screening
Visit V2: Trial day 0**	Day 0	Treatment period
Rescheduled day 0	R1-Day 0, R2-Day 0, etc.	
Visit V3: Trial day 7 ± 1**	Day 7	
Rescheduled day 7	R1-Day 7, R2-Day 7, etc.	
Visit V4: Trial day 14 ± 1**	Day 14	Follow-up
Rescheduled day 14	R1-Day 14, R2-Day 14, etc.	
Visit V5: Trial day 35 ± 2	Day 35	
Visit V6: Trial day 60 ± 5	Day 60	Follow-up
Visit V7: End of trial, trial day 104 ± 10	Day 104	
Unscheduled visits: A patient with a treatment induced or treatment boosted ADA response at visits 3-7 must be called in for an unscheduled visit	ADA-V1, ADA-V2, etc.	Unscheduled ADA visits

Time points will be abbreviated following the eCRF (e.g. pre-dose, 30min, 90min etc.).

* There could possibly be re-screening visits. In such a case only the latest screening visit will be tabulated. However data from each screening and re-screening – if available - will be listed.

** Note that there can possibly be a re-scheduling of the dosing days in case of meeting any dosing day exclusion criteria. The dosing day with the most recent date will be used for analyses as the ‘trial day’ (e.g. for display of results in tables or in case of baseline value determinations) unless not otherwise specified. In some cases results from all re-scheduled visits have to be considered. This will be indicated in the respective sections of the SAP. All data from dosing day visits will be listed.

7.3 Subgroup/ Stratification terminology

The following subgroups will be used for analyses:

Subgroup/ Stratification	Notation as used throughout all tables, listings and figures
Patients with previous exogenic glucagon exposure will not be excluded from the trial, but the information on previous glucagon administration will be recorded in the eCRF section ‘Concomitant medication’ at screening. (PT= Glucagon, ATC= H04AA)	Previous exogenic glucagon exposure
Age class: Patients are included in the trial having an age at giving at informed consent between 18 and 70. Age at informed consent will be categorized into classes: 18–40, 41–64, 65-70. Reasonable patient distribution in age classes will be discussed with the sponsor and a decision upon the final cut-offs will be made using blinded data.	Age class
Gender: Subgroup analyses will be performed for males and females	Gender
Race: Race classification can be done using categories 1= american indian or alaska native, 2= asian, 3= black or african american, 4= native hawaiian or other pacific islander, 5= white, 99= other. In case multiple answers are given, the categories will be combined.	Race
ADA positive at baseline: Patients having a positive ADA at baseline.	Baseline ADA positive
ADA negative at baseline: An ADA-negative subject is a subject not being ADA-positive at baseline.	Baseline ADA negative

8. ANALYSIS POPULATIONS/ ANALYSIS SETS

The following patient populations will be used for the analyses as specified afterwards:

- All patients analysis set (ALL):** The ALL patient set includes all patients having been enrolled.
- Safety set (SAS):** The safety analysis set consists of data for all patients who were randomized and received at least one dose of trial medication.

3. **Full analysis set (FAS):** The full analysis set is defined as all patients of the SAS population with at least one measurement of the ADA titer at baseline (screening).
4. **Per Protocol set (PPS):** The PPS consists of all patients of the FAS for whom no relevant protocol deviations were documented.
5. **PK/PD set (PKS):** All patients in the SAS having at least one pre- and post-dose PK value at one visit.

The decision whether a protocol deviation is relevant or not for the exclusion of patients from the PPS set will be made case-by-case in a data review meeting before unblinding.

Assignment of analysis populations to analyses:

1. **ALL:** Presentation of information under sections study population (e.g. patient disposition, except termination/ withdrawal information).
2. **FAS:** Analysis of the primary endpoint, the key secondary endpoints and secondary endpoints referring to ADA response characterizations.
3. **SAS:** Safety parameters and analysis of study drug administration/ extent of exposure and termination/ withdrawal information.
4. **PKS:** Pharmacokinetic and pharmacodynamics endpoints

Main conclusions of the primary endpoint will be drawn from analyses based on the FAS. A secondary analysis of the primary endpoint will be based on the PPS.

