7.6.1 Immunogenicity measurements

Antibodies against dasiglucagon/glucagon will be measured at all visits after screening. During the treatment period (Visits 2, 3, and 4) samples will be collected pre-dose as well as at unscheduled dosing visits for ADA positive patients.

The ADA samples will be analyzed at a special laboratory (refer to Appendix 1). Samples collected at the planned visits will be analyzed in batches at three occasions during the trial and any positive results will immediately be communicated to the investigator in a blinded manner.

The clinical ADA assays have been validated in accordance with existing guidelines and recommendations.^{6,7,8,9,10}

Confirmed positive anti- dasiglucagon antibody samples, (treatment-induced or treatment-boosted) from anti-dasiglucagon antibody-positive patients will be evaluated for binding titer neutralizing potential and titer as well as cross-reactivity towards endogenous glucagon.

No further serum sampling will be needed as the ADA samples can be used for Nab analysis.

The *in vitro* neutralizing effect of antibodies will be measured using an assay^{9,12} based on glucagon receptor transfected human embryonic kidney cells. The calculated sensitivity in previous studies was about 51.8 ng/mL. The assay was also validated for recombinant glucagon with similar results.^{11,12} In case of a positive result in the Nab assay, a titer estimation will be performed. The cell-based Nab analyses will be performed by a special laboratory, BioAgilytix, Durham, NC, USA.

In vivo neutralizing effect will be evaluated by comparing PK and PD endpoints between ADA positive and ADA negative patients, further investigation may be performed by correlating ADA titer with PK and PD endpoints.

Residual and additional antibody serum samples may be stored until approval of market authorization by the health authorities. Further characterization of the antibody response may be requested by the health authorities.

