10.1.2 Classification of patients to subsets

For the statistical analysis the randomized patients will be divided up into the following datasets:

The following definitions are applicable:

Safety analysis set (SAS)	all patients who were randomized and received at least one dose of trial medication
Full analysis set (FAS)	all patients of the SAS with at least one measurement of the ADA titer at baseline
Per Protocol set (PPS)	all patients of the FAS for whom no relevant protocol deviations were documented

The analysis of the primary endpoint will be based on the FAS. A secondary analysis of the primary endpoint will be based on the PPS. Safety analysis will be based on the SAS.

The decision whether a protocol deviation is relevant or not for the exclusion of patients from the PPS set will be made case-by-case in a data review meeting.

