Clinical (adverse) event of interest	
A clinical event of interest is an event which, in the evaluation of safety, has a special focus (e.g. required by health authorities). They will be recorded under the eCRF section adverse events.
 
In this trial hemodynamic changes, as defined below, are considered clinical events of interest:
 
• Post-dose clinical signs or measured vital signs indicating a clinical significant drop in blood pressure including signs of orthostatic hypotension, vasovagal responses or bradycardia.• Post-dose change in pulse or blood pressure considered an event of hypo- or hypertension as judged by the investigator.
ADA titer	A sample is defined as ADA-positive if results of the screening and confirmatory assays are positive. If positive, a titer (the reciprocal of the highest dilution factor that still yields a positive reading, e.g. dilution 1/10 = titer 10) will be reported. Any titer above zero defines positivity.
ADA-positive/ negative-subject (after baseline)	ADA-positive after baseline is a subject with at least one treatment-induced or treatment-boosted ADA positive sample at any time during the treatment or follow-up observation period. In contrast a ADA-negative subject after baseline is a subject without any treatment-induced or treatment-boosted ADA-positive sample at any time during treatment or follow-up.
Evaluable patients	A subject with at least one sample taken after drug

	
administration during the treatment or follow-up that is appropriate for ADA testing (with reportable result). This is the same definition as for the FAS population. Only evaluable subjects are considered for computing treatment-induced ADA incidence

Pre-existing/ baseline ADA	
Refers to antibodies reactive with the biologic drug that are present in subjects before treatment or before the initiation of the study.

Treatment-induced ADA	
ADA developed de novo (sero-conversion) following biologic drug administration (i.e., formation of ADA any time after the initial drug administration in a subject without pre-existing ADA).

Treatment-boosted ADA	
Pre-existing ADA that were boosted to a higher level following biologic drug administration (i.e., any time after the initial drug administration the ADA titer is greater than the baseline titer by a scientifically reasonable margin - in this study the fifth fold increase.

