11.3 Baseline treatment values

ADA status measured in serum and ADA antibody serum sample results for immunogenicity measurements at day 0 pre-dose will serve as baseline.

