3.1 Definition of analysis populations

The Study Protocol and the Statistical Analysis Plan (v0.2) detail the following analysis sets:

1. **All patients analysis set (ALL)** includes all patients that have been enrolled.
2. **Safety set (SAS) includes** all patients who were randomized and received at least one dose of trial medication.
3. **Full analysis set (FAS)** is defined as all patients included in the SAS population with at least one ADA measurement at baseline (Visit 2).
4. **Per Protocol set (PPS)** consists of all patients included in the FAS for whom no relevant protocol deviations were documented
5. **PKPD set (PKS)** is defined as all patients included in the SAS with at least one pre- and post-dose PK/PD value at one visit (Visit 2/4).

Assignment of analysis populations to analyses:

The study population including information on subject disposition and protocol deviations will be presented based on the ALL analysis set.

Analysis of primary endpoint, key secondary endpoints and secondary endpoints referring to ADA response characterizations will be made for the FAS analysis set.

A secondary analysis of the primary endpoint will be based on the PPS.

The SAS set will be used to analysis safety parameters and study drug administration/extent of exposure.

The PKS set will be used for the analysis of pharmacokinetic and pharmacodynamics endpoints.

Adherence to the study protocol is defined based on defined protocol deviation categories. The decision whether a subject adhered to the protocol was made by classifying reported and/or derived deviations into major and minor protocol deviations.

Major protocol deviations led to exclusion from the PP set.

The decision whether a protocol deviation is major or minor was done at the Blind Data Review Meeting.

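### The SAP ties the primary-endpoint analysis set to an ADA titer at screening, where no ADA sample is taken, and wrongly equates that set with the evaluable patients, leaving two possible denominators

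*SAP*

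**What the plan says.** **The analysis set.** SAP Section 8, item 3, defines the FAS as treated, randomized patients "with at least one measurement of the ADA titer at baseline (screening". The same section says: "Main conclusions of the primary endpoint will be drawn from analyses based on the FAS". Protocol version 3, Section 10.1.2, has "all patients of the SAS with at least one measurement of the ADA titer at baseline", with no mention of screening.

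**When ADA is sampled.** In the SAP visit table (7.2), the screening label belongs to Visit 1 alone: "Visit V1: Screening visit*, trial day -3, visit window (-30 to -3". Visit 2 is Day 0. Protocol 7.6.1 says "Antibodies against dasiglucagon/glucagon will be measured at all visits after screening", and both flow charts show the first antibody sample at Visit 2. SAP 11.3 states that the ADA results "at day 0 pre-dose will serve as baseline". The data review meeting document, filed with the SAP, words the FAS differently in its Section 3.1: "with at least one ADA measurement at baseline (Visit 2".

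**The evaluable set.** The SAP Definitions call a patient evaluable if at least one sample taken after dosing gives a reportable ADA result. They then add: "This is the same definition as for the FAS population". SAP 12.1 repeats the post-dose definition and divides the primary numerator by the number of evaluable patients. Appendix C lists the primary tables on the FAS and the per-protocol set.

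**The concern.** Two rules that fix the primary denominator are wrong as written.

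The first is the bracketed word in Section 8, which places the qualifying measurement at a visit without ADA sampling.

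The second has more effect on the analysis. One definition looks only at baseline and the other only after dosing, yet the SAP says they are the same. A programmer who relies on that sentence can take the FAS as the denominator without checking for post-dose data. Baseline-negative patients who were never tested after dosing would then count as patients without an ADA response. The reported incidence would be too low and its upper limit too tight, which on a safety endpoint is the direction that flatters the products.

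**Working it through.** **Step 1: set the definitions side by side.**

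| Place | Baseline ADA result required? | Post-dose ADA result required? |
|---|---|---|
| SAP 8, FAS | Yes, glossed as screening | No |
| Protocol 10.1.2, FAS | Yes | No |
| Data review document 3.1, FAS | Yes, at Visit 2 | No |
| SAP Definitions and 12.1, evaluable | No | Yes |

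The FAS and the evaluable set coincide only if every FAS patient has a post-dose result and every evaluable patient has a baseline result. This is so whichever visit is called baseline, so correcting the word screening does not rescue the equality.

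**Step 2: check whether the exclusion clause closes the gap.** The primary endpoint (SAP 11.1 and 12.1) removes baseline-positive patients who have no post-dose sample. If the denominator is the evaluable set, the clause is redundant, because those patients are already out. If the denominator is the FAS, the clause removes only the baseline-positive ones, and baseline-negative patients without post-dose data stay in.

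**Step 3: reproduce the plan's own figure.** SAP Section 5 gives 45 completers per arm.
- ln(0.10)/ln(0.95) = 44.89, rounded up to 45.
- Chance of at least one event at a true rate of 5%: 1 − 0.95^45 = 0.9006.
- Upper bound with 0 of 45: 1 − 0.10^(1/45) = 4.99%.

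The 45 is reproduced, and this point does not change it. The 4.99% is a one-sided 90% bound, whereas the planned tables show 95% intervals. The limits below are therefore on a different scale from the planning figure.

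**Step 4: size the effect on the denominator.** Inputs:
- 112 randomized 1:1 gives 112/2 = 56 per arm (SAP 4 and 5).
- The limits are taken as exact two-sided 95%. SAP 12.1 specifies exact limits for the difference; applying the exact method to each arm is my assumption.
- The number m of baseline-negative patients in an arm with no post-dose result is not given. I assume 1, 3, 6 or 11, where 11 = 56 − 45 is the planned gap between randomized patients and completers.

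With 0 events the upper limit is 1 − 0.025^(1/n).

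| m (assumed) | FAS n | Upper limit, FAS | n with post-dose result | Upper limit |
|---|---|---|---|---|
| 1 | 56 | 6.38% | 55 | 6.49% |
| 3 | 56 | 6.38% | 53 | 6.72% |
| 6 | 56 | 6.38% | 50 | 7.11% |
| 11 | 56 | 6.38% | 45 | 7.87% |

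With events, at m = 3: 1/56 = 1.79% (upper limit 9.55%) against 1/53 = 1.89% (10.07%); 2/56 = 3.57% (12.31%) against 2/53 = 3.77% (12.98%).

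**The case against.** The strongest reply is that the documents, read together, give the right set. SAP 11.3, protocol 10.1.2 and the data review document all point to Day 0. SAP 12.1 restates the post-dose requirement where the division is described. Applying FAS membership first and the evaluable rule second yields patients with both a baseline and a post-dose result. Few patients should lack a post-dose sample: the first is due at Day 7, and protocol 7.3.3.1 asks patients who discontinue after dosing to return on Days 35, 60 and 104. The analysis is descriptive.

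Much of this stands, and it rules out four stronger readings that a reader might infer:

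- *The FAS is empty.* Only a literal reading of one bracketed word gives that. SAP 11.3 and the data review document show that Visit 2 was meant.
- *Requiring a titer leaves out ADA-negative patients.* The Definitions treat any titer above zero as positive, so a negative can be held as zero. The primary analysis itself needs baseline-negative patients in the set.
- *Patients without post-dose data automatically count as negative.* SAP 12.1 and the valid-cases rule in SAP 9 point the other way. Dilution arises only if the FAS is taken as the denominator.
- *The key secondary incidences need the same denominator.* SAP 12.2.1 and 12.2.2 base them on baseline-negative and baseline-positive patients respectively. Nothing here justifies overriding that.

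The reply does not remove the two errors. The SAP nowhere says to intersect the two sets, and it tells the reader that no intersection is needed because they are the same. The data review document treats a missed ADA sample as a major deviation, but that protects only the per-protocol analysis, not the FAS analysis on which the main conclusions rest.

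**Conclusion.** The point holds as a correction to the rule for the primary denominator. The screening gloss in SAP 8 contradicts the sampling schedule and SAP 11.3. The statement that the evaluable set and the FAS share a definition is false under any reading of baseline. Together they leave the primary overall ADA incidence open to two denominators.

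The numerical effect is small if few samples are missing. With 0 events and 3 of 56 patients in an arm lacking post-dose data, the upper limit moves by 6.72 − 6.38 = 0.34 percentage points. Over the assumed range of 1 to 11 patients, the limit on those with post-dose results is 6.49% to 7.87%, against 6.38% on the FAS. These sizes rest on assumed counts, since the documents give none, and on 56 patients per arm. The direction does not depend on the count: using the FAS can only lower the incidence or leave it unchanged, and tighten its upper limit.

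**What to change.** Make four changes to the SAP text.

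1. In Section 8, item 3, require a reportable ADA result (positive or negative) at Day 0 pre-dose (Visit 2), in place of a titer at baseline with the screening gloss.
2. In the Definitions, delete the sentence that equates evaluable patients with the FAS.
3. In Section 12.1, state that the denominator for the primary overall ADA incidence is FAS patients with at least one reportable post-dose ADA result. Leave the key secondary denominators as they are.
4. In Section 20.2, which now records no changes, note any departure from the FAS wording in protocol 10.1.2.

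The cost is wording only, with no new data and no change to sample size. Protocol 10.1 allows the SAP to adapt the planned analysis before unblinding, so the correction belongs there.
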